After sensing the participant's normal respiratory pattern, the active device will begin to play a distinct musical tone to prompt inspiration and a second tone to prompt expiration. The device will first synchronize its tones to the user's spontaneous respiratory pattern, and then gradually increase the timing and duration of its tones to guide the user in slowing her respiratory rate and prolonging her expiratory phase. The participant will be instructed to simply try to match her inspiration and expiration to the tones. Participants will be asked to use the RESPeRATE device for at least 15 minutes per day at home while sitting quietly and alone in a comfortable location, not listening to other music, watching television, reading, sleeping, or performing any other distracting activity.

During practice sessions, the active device will automatically collect data on: a) the time, date, and number of sessions in which it was used; b) duration of time for each practice session; c) average and range of respiratory rate; d) data quality (i.e., percent time that breathing was detected by the sensor), e) amount of time

that the participant succeeds in slowing respiration to less than 10 BPM in each session, and f) the percentage of time that the participant's breathing pattern follows the device's musical tones. Participants will be instructed to use RESPeRATE for at least 15 minutes per day for a total of 12 weeks.

D.4.3 Control intervention

Participants who are randomized to the control group will use a control RESPeRATE device that does not pace respiration, but plays relaxing, non-rhythmic music while monitoring participants' spontaneous breathing rate at home. RESPeRATE devices can be re-programmed by research staff to be either active or control devices using software provided by Intercure, Ltd., and research staff will re-program devices as needed at participants' baseline visits. The control device will look exactly like the active RESPeRATE device, except that the device will not play musical tones synchronized to inspiration and expiration, but will play quiet, non-rhythmic music while monitoring spontaneous breathing.

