Like participants in the active group, participants in the control group will be asked to use their devices for at least 15 minutes per day for 12 weeks. Participants in the control group will be given the same instructions as those randomized to use the active RESPeRATE device, except that they will be told to simply listen to the music played by the device rather than using the device as a guide for breathing. Like the active device, the control device will automatically collect data on: a) time, date, and number of sessions in which it was used; b) duration of time for each session; c) average and range of respiratory rate, and d) data quality (i.e., percent time that breathing was detected by the sensor).

This control device will control for the fact that participants will be sitting still and relaxing while wearing the RESPeRATE device breathing sensor belt for at least 15 minutes per day. It will also allow collection of data on spontaneous breathing pattern in the control group and monitoring of adherence to use of the control intervention.

D.4.4 Randomization

Randomization to either the active or control device will be performed by computer at a 1:1 ratio, using randomly permuted blocks of 2, 4, and 6. Following a brief run-in period in which women use the control device and complete other eligibility assessment procedures, women will be randomized either to: 1) receive a new active RESPeRATE device that paces respiration at a slow rate, or 2) continue using a control device that monitors spontaneous breathing rate while playing non-rhythmic music. Sealed, opaque envelopes will be prepared by the study statistician containing treatment assignment codes. When a participant fulfills study inclusion and exclusion criteria, the next sequential envelope will be opened by study staff and treatment assignment will be irrevocably entered on a participant case report form. A subset of the randomization envelopes will be assigned to the Oakland Satellite office.

D.4.5 Blinding

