- B. Cognitive anxiety: Cognitive anxiety (i.e., the mental component of anxiety associated with fear of failure) will be measured by the Hospital Anxiety and Depression Scale (HADS), a validated self-administered questionnaire that includes a 7-item Anxiety Subscale⁴⁹ shown to be sensitive to change in incontinence trials.⁵⁰ Scores range from 0 to 21, with higher scores indicating greater anxiety.
- C. Depressive symptoms: Depressive symptoms will be assessed by the Center for Epidemiologic Studies Depression Scale, a 20-item measure that has been widely used in clinical trials, including trials of bladder interventions, and is sensitive to change.⁵¹ Total scores range from 0 to 60, with higher scores indicating greater likelihood of depression.
- D. Perceived stress: Perceived stress will be assessed using the Cohen Perceived Stress Scale (PSS), a 10-item self-administered questionnaire assessing subjective feelings and thoughts related to perceived stress in the past month, validated in a probability sample of the United States.⁵² Scores range from 0 to 40, with higher scores indicating greater perceived stress.

D.5.4 Respiratory parameters

Respiratory parameters will be measured daily throughout the study by participants' RESPeRATE devices. The RESPeRATE device automatically collects data on respiratory parameters such as average and range of respiratory rate during each practice session. Additionally, the active RESPeRATE device collects data on effectiveness of slow-paced respiration (minutes of breathing in each session in which the respiratory rate was under 10 BPM) and device 'followness' (percent time that breathing was synchronized with the guiding tones). Data are downloaded directly from the device, providing an objective and blinded measurement of respiratory status during sessions. Decrease in respiratory rate with preserved 'followness' indicates that a participant has successfully paced her respiration at a lower rate without holding her breath, and is associated with improvement in blood pressure in prior research⁵³.

D.5.5 Actigraphy (assessed at baseline and at 12 weeks at the [name] site only)

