Because previous studies of RESPeRATE for other indications have shown that efficacy improves with adherence,^{57,60} all women will complete a 7-day run-in period between the screening and baseline visits in which they will demonstrate willingness to adhere to home RESPeRATE practice. For the run-in, women will be given a demo RESPeRATE run-in device that plays relaxing, non-rhythmic background music but does not pace their breathing. The music played by the demo run-in RESPeRATE devices will be similar but not completely identical to the music played by the regular RESPeRATE control devices that serve as the main control intervention for the study. Like the regular RESPeRATE control device, the demo RESPeRATE control device will automatically collect data on: a) time, date, and number of sessions in which it was used; b) duration of time for each session; c) average and range of respiratory rate during each session; and d) data quality (i.e., percent time that breathing was detected by the sensor). Women will be told to use their run-in RESPeRATE devices for at least 15 minutes each day during the run-in period, while sitting quietly and alone in a comfortable location, and avoiding listening to other music, watch TV, read, sleep, or perform any other distracting activity. For at least 3 days during the run-in period, women will also complete daily voiding diaries, which will be used to further assess women's compliance and to collect data on baseline severity of overactive bladder symptoms. Women will also be asked to wear a wrist actigraph while they complete their voiding diaries, push a button on the actigraph to indicate when they go to bed and when they get up each night, and complete a simple sleep diary over this same 3-day period.

D.6.4 Baseline/Randomization Visit

A baseline visit will be scheduled one to two weeks after the screening visit and completion of the run-in procedures. Participants will return with their completed voiding diary, the demo RESPeRATE run-in device, and the wrist actigraph and sleep diary. Diary data will be abstracted, and data from the run-in device and the actigraph will be downloaded. Those who are non-adherent to RESPeRATE practice or the diary will not be eligible to continue. Blood pressure, heart rate, and respiratory rate will be re-measured; participants who have a blood pressure <100/60 will also be ineligible to continue. If the demo RESPeRATE device indicates

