home practice for at least 12 minutes on each of at least 6 days, the voiding diary is completed correctly on at least 3 days, and the diary reveals an average of at least 3 voiding or incontinence episodes per day associated with at least moderate urgency, and the participant meets other eligibility criteria and agrees to enroll in the study, she will be eligible for randomization to a regular active or control RESPeRATE device. Immediately following proof of eligibility, the study coordinator will randomize the participant, using the next sequential randomization envelope.

Following randomization, instruction in use of the active or control RESPeRATE device will be reviewed, and the participant will be asked to use the device for at least 15 minutes per day at home. The participant will be given the study phone number and instructed to call study staff for any questions or problems with the devices. Participants will be given a pamphlet providing brief information about usual care behavioral self-management of overactive bladder symptoms. Participants will be reminded not to take any medications known to affect overactive bladder symptoms during the treatment period.

Participants will also undergo non-invasive measurement of resting heart rate variability and pre-ejection period using the BIOPAC MP150 monitoring device at this visit (if they are randomized). They will complete questionnaires assessing condition-specific quality of life and anxiety and perceived stress symptoms.

D.6.5 Follow-up Visit (1 week)

After one week of treatment, participants will return to the clinic for early follow-up, bringing their RESPeRATE active or control devices. Downloaded RESPeRATE device data will be securely transferred to the study database. The study coordinator will review adherence with use of the active or control device, assess for side effects of treatment, and answer any questions. For safety monitoring, blood pressure, heart rate, and respiratory rate will be reassessed by study staff. Adverse events will be recorded on standardized forms. Each participant will also be given a new, blank voiding diary to complete for 3 days before her 6-week visit.

D.6.6 Follow-up Visit (6 weeks)

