analyses, we will also assess for a dose response in cumulative time of effective breathing practice, by examining the relationships between total minutes of effective practice and OAB outcomes at 12 weeks, controlling for baseline levels of outcomes. These analyses will allow for assessment of the extent to which differences in adherence and treatment exposure influence treatment benefits on OAB.

D.10.5 Subgroup analyses

Differences between treatment groups will be analyzed in pre-defined subgroups based on clinicopathologic factors in multivariate analysis. For example, we will explore whether high baseline levels of autonomic imbalance or anxiety, past use of medications or other OAB treatments, or baseline use of psychoactive medications influence treatment-associated changes in outcomes. Subgroup-specific effect estimates will be considered only if the interaction with the subgroup is significant at $p < 0.05$.

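### The exploratory cumulative-minutes analysis in D.10.4 is an observational active-arm slope adjusted only for the baseline outcome, so it cannot show how far exposure influences treatment benefit.

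*Combined protocol and SAP*

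**What the plan says.** D.10.4 has two parts. The first is a closed test of duration: if the 12-week benefit is significant, change from baseline to 6 weeks and from 6 to 12 weeks is tested. The second is labelled exploratory and studies dose response in cumulative time "by examining the relationships between total minutes of effective practice and OAB outcomes at 12 weeks, controlling for baseline levels of outcomes". No arm term, restriction to one arm or further covariate is given. The section closes: "These analyses will allow for assessment of the extent to which differences in adherence and treatment exposure influence treatment benefits on OAB".

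The exposure is described elsewhere:

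- D.4.2 lists, for the active device, the time "that the participant succeeds in slowing respiration to less than 10 BPM in each session". D.5.4 says that "the active RESPeRATE device collects data on effectiveness of slow-paced respiration (minutes of breathing in each session" with the rate under 10 BPM.
- D.4.3 lists for the control device the sessions, their duration, "c) average and range of respiratory rate, and d) data quality (i.e., percent time that breathing was detected by the sensor". Effective minutes are not on that list.

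Before randomisation, D.6.3 has the run-in device log "b) duration of time for each session; c) average and range of respiratory rate during each session" for every woman, and D.6.4 has these data downloaded at baseline. D.6.4 uses them for eligibility: "home practice for at least 12 minutes on each of at least 6 days". D.2 also excludes women whose resting rate is already below 10 as measured during run-in.

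**The concern.** A woman's effective minutes depend on what she does after assignment. Women who practise more may also differ in motivation, anxiety or early symptom response. They may make more use of the pamphlet techniques, which D.4.6 expects to be used alongside the breathing. Any of these can improve the 12-week diary without the minutes being the cause. Randomisation does not protect a comparison of high and low users within one arm, and the baseline diary count captures only part of the difference.

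The closing sentence of D.10.4 nevertheless speaks of exposure influencing treatment benefit, which is a causal reading. At stake is one exploratory statement: a reader could take a slope produced by the kind of woman who practises as evidence that more minutes bring more benefit.

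**Working it through.** **Step 1: which comparison is it?** Effective minutes appear in the active list (D.4.2, D.5.4) and not in the control list (D.4.3), so the natural reading is a slope within the active arm. The plan does not say this. If instead the arms were pooled with control minutes set to 0 and no arm term, minutes would largely stand in for arm. Simulated with a constant 2.4-episode arm effect unrelated to minutes (20% of the D.10.2 mean of 12), that model shows a false dose response in about 57-72% of trials (assumed coefficient of variation of minutes 0.5 to 0.25). Naming the active arm removes this reading.

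**Step 2: does another section supply the adjustment?** No. D.5.6 covariates guide adjustment only if the treatment groups are unbalanced. D.10.3 adjusts for differential dropout. Anxiety and autonomic status enter the mediation models (D.10.1) and subgroup analyses (D.10.5). Run-in data restrict entry but are not covariates in this model.

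**Step 3: how large could the distortion be?** The plan gives no figure to reproduce for this analysis. Inputs from D.10.2 are 80 per arm, 15% loss, SD of change 5.8 and correlation 0.59. Equal variances at both times are assumed.

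- Active completers: 80 × 0.85 = 68.
- SD of the outcome: 5.8 / √(2 × (1 − 0.59)) = 6.41.
- Residual SD after baseline adjustment: 6.41 × √(1 − 0.59²) = 5.17.
- Degrees of freedom: 68 − 3 = 65; t = 1.997. Critical partial correlation: 1.997 / √(1.997² + 65) = 0.24.
- False slope per SD of minutes: correlation × 5.17, so 0.52, 1.03 and 1.55 episodes at 0.1, 0.2 and 0.3.

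Simulated share of trials with p < 0.05 and no true dose effect:

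| Assumed correlation of minutes with residual outcome | Baseline outcome only |
|---|---|
| 0 | 5% |
| 0.1 | 13% |
| 0.2 | 37-38% |
| 0.3 | about 70% |

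These correlations are with the whole residual outcome. If one factor correlates r with minutes and r with the residual outcome, the induced correlation is only r²:

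| r | Induced correlation | Share significant |
|---|---|---|
| 0.2 | 0.04 | about 6% |
| 0.3 | 0.09 | about 12% |
| 0.4 | 0.16 | about 26% |
| 0.5 | 0.25 | about 54% |

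**Step 4: what do the run-in data change?** Assume that the entry rule removes the lowest 10-30% on run-in use, and that run-in use correlates 0.5-0.7 with the trait behind the confounding.

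| Correlation before the entry rule | After the rule, baseline only | Run-in use added |
|---|---|---|
| 0.2 | 25-35% | 15-26% |
| 0.3 | 51-66% | 30-52% |

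The entry rule helps a little. The covariate helps more, but neither brings the rate back to 5%.

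**Step 5: should run-in respiratory rate be added too?** D.4.2 says that the device matches the user's "spontaneous respiratory pattern, and then gradually increase the timing and duration of its tones to guide the user in slowing her respiratory rate". A woman who starts slower may therefore log more effective minutes at equal use. That links rate to minutes, but the documents show no link from rate to OAB outcome. If rate predicts minutes only (correlation 0.3-0.5, assumed), adding it raises false positives from about 37% to 40-48% at 0.2 and from about 70% to 74-82% at 0.3. At a rate-minutes correlation of 0.5 the false slope grows by about a third (from about 1.0 to 1.4 episodes at 0.2).

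**The case against.** The strongest reply is that the plan promises little here. The analysis is called exploratory, it is conditional on a 12-week benefit, and no alpha is attached to it; the 0.05 in D.10.4 belongs to the duration test. The closing sentence also covers both analyses, so it is not a claim about this slope alone. All of this stands and keeps the severity low. It does not remove the problem: the exploratory label concerns confirmatory status and does not make an observational slope show influence on benefit. Conditioning on a significant primary result hardly changes the illustration (12.5%, 36.7% and 70.1% at 0.1, 0.2 and 0.3).

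Three stronger readings are tempting, and the documents do not support them.

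- A reader might infer that the run-in data are not used at all. They are: D.6.4 restricts entry on use and D.2 on resting rate. They are only absent from this model.
- A reader might infer that fuller adjustment would rescue the causal statement. It would not: after run-in use is added, false positives remain above 5% in every scenario of Step 4.
- A reader might take 37% or 70% as the expected error rate of this trial. The documents give no correlation between minutes and outcome, and a weak shared factor gives 6-12%.

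**Conclusion.** The point holds as a limit on interpretation. The cumulative-minutes analysis can describe an association among women given the active device; it cannot show how far cumulative exposure changes treatment benefit. That follows from the design and needs no assumed number. Leaving run-in use out of the model is a smaller, separate weakness: adding it lowered false positives in every scenario checked, but only in part.

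The percentages are illustrations. They rest on assumed correlations, equal variances, 68 active completers and a 5% test that the plan does not specify. A reader might infer that the efficacy conclusions are at risk. They are not: the primary analysis is by intention to treat without regard to adherence (D.10.1), and the duration test compares time periods rather than self-selected doses. This is an optional improvement.

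**What to change.** In D.10.4:

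1. State that the cumulative-minutes analysis is in the active arm only.
2. Add run-in minutes of device use beside the baseline outcome.
3. Say that the result will be reported as a hypothesis-generating association.
4. Narrow the closing sentence so that it claims no effect of cumulative exposure on benefit. The duration test and its wording can stay.

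Do not add run-in respiratory rate as a routine covariate; at most use it in a sensitivity analysis. Do not substitute an arm-by-minutes interaction. Its power is only 10-26% if a mean benefit of 2.4 episodes is truly proportional to minutes (assumed coefficient of variation 0.25 to 0.5). Its false-positive rate is 21-41% if minutes correlate 0.3 with the residual outcome in one arm and 0.1 or 0 in the other.

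The cost is two reworded sentences and one degree of freedom (65 to 64). The run-in minutes are already downloaded at baseline, so no data, visits or participants are added. The limitation that remains is that adjustment reduces the confounding only in part, which is why the wording has to change as well.

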- 2) Report recurrent episodes of urgency (sudden or strong urges to urinate) beginning at least 3 months prior to screening
- 3) Able to record all voiding and incontinence episodes on a screening 3-day voiding diary^{29,30} and rate the severity of urgency associated with each episode using a validated urgency severity scale³¹
- 4) Document at least 9 voiding or incontinence episodes on the above 3-day voiding diary that are associated with at least moderate sensation of urgency (using the above validated urgency severity scale)³¹
- 5) Willing to refrain from initiating other treatments that may affect voiding pattern during the trial period

Exclusion criteria

- 1) Use of anticholinergic OAB medications or other medications known to affect urinary function (i.e., diuretics, tricyclic antidepressants) within 1 month of screening
- 2) Current urinary tract infection (detected via screening dipstick urinalysis or urine culture) or a history more than 3 urinary tract infections in the preceding 1 year
- 3) Prior history of lower urinary tract surgery, pelvic cancer, or pelvic irradiation; or other pelvic or abdominal surgery within 6 months of screening
- 4) History of interstitial cystitis, fistula in the bladder or rectum, or congenital or childhood defect leading to chronic urinary incontinence, retention, or other chronic urinary symptoms

- 5) Known history of major neurologic conditions likely to have major or permanent effects on bladder function such as stroke, multiple sclerosis, spinal cord injury, or Parkinson's disease
- 6) Use of bladder botulinum injections, electrostimulation, or other invasive therapies for OAB or incontinence within 3 months of screening
- 7) Formal pelvic floor rehabilitation or other formal behavioral therapy for bladder symptoms involving a physical therapist or other certified practitioner within 3 months of screening
- 8) Started, stopped, or changed dosage of a psychoactive medication likely to affect anxiety (SSRIs/SNRIs, tricyclics) within 3 months of screening, or plans to start, stop, or change dosage during the trial
- 9) Resting blood pressure (average of 2 measures) less than 100/60 at screening (women with baseline low blood pressure may theoretically be at increased risk of hypotension with use of RESPeRATE)
- 10) Resting breathing rate already below 10 breaths/minute before treatment (as measured during run-in)

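### The dose-response exposure in D.10.4 (minutes under 10 BPM) depends partly on each woman's starting breathing rate, which the model leaves out

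*Combined protocol and SAP*

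**What the plan says.** If treatment appears effective at 12 weeks, D.10.4 (Dose effects) adds an exploratory analysis of cumulative practice, "examining the relationships between total minutes of effective practice and OAB outcomes at 12 weeks, controlling for baseline levels of outcomes". The result is to be read as showing "the extent to which differences in adherence and treatment exposure influence treatment benefits on OAB".

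D.10.4 does not define effective practice. Two other sections supply the meaning:

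- D.5.4 explains the device's effectiveness measure as "minutes of breathing in each session in which the respiratory rate was under 10 BPM".
- D.4.2 lists, among the data the active device stores, the time "that the participant succeeds in slowing respiration to less than 10 BPM in each session".

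Neither asks for a minimum fall from the woman's own rate. On how the rate comes down, D.4.2 says the device first matches its tones to her spontaneous breathing and will "then gradually increase the timing and duration of its tones to guide the user in slowing her respiratory rate".

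Exclusion criterion 10 in D.2 removes women whose run-in rate is already below 10 breaths per minute. The run-in device records "average and range of respiratory rate during each session" (D.6.3), so a pre-randomization breathing rate exists for every woman. It does not appear in the D.10.4 model.

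**The concern.** Consider two women who practise on the same days, for the same time, and follow the tones equally well. One starts at 11 BPM and crosses the 10 BPM line early in the session. The other starts at 18 BPM and must come down 8 BPM before her first minute counts. Their recorded doses differ although their adherence does not.

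This matters for how the slope is read:

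- If benefit follows the amount of slowing, women with the largest falls may carry the smaller recorded doses, and a real dose response would be blunted.
- If starting rate itself predicts the 12-week outcome, the slope absorbs that association and is biased.

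In either case the slope mixes starting rate with adherence and exposure.

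**Working it through.** **Inputs from the document.** Sessions of at least 15 minutes a day for 12 weeks (D.4.1); an effective minute is one under 10 BPM (D.5.4); slowing is gradual from the woman's own rate (D.4.2); women enter at 10 BPM or above (D.2).

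**Not in the document.** The speed of slowing, the rate finally reached, and any SD of breathing rate. The only typical value is a resting rate of 14 BPM in section C. Everything below that needs these inputs is an illustration.

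**The plan's own figure.** 15 min × 84 days = 1,260 min = 21 hours, as D.6.10 states. This is the ceiling of the exposure at the minimum session length.

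**Constant-speed illustration.** A perfect follower starts at S and slows by v BPM per minute to 8 BPM. She crosses 10 BPM after (S − 10)/v minutes, so effective minutes per session are E = 15 − (S − 10)/v, or 0 if that is negative.

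| v (BPM/min) | S = 11 | S = 14 | S = 18 |
|---|---|---|---|
| 1.5 | 14.3 | 12.3 | 9.7 |
| 1.0 | 14.0 | 11.0 | 7.0 |
| 0.5 | 13.0 | 7.0 | 0.0 |

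Over 84 sessions at v = 1.0, starts of 11 and 18 give 14.0 × 84 = 1,176 and 7.0 × 84 = 588 minutes, with identical adherence.

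**Slowing in the same sessions.** With the floor of 8 BPM reached inside the session, cumulative slowing is 15(S − 8) − (S − 8)²/(2v) BPM-minutes. At v = 1.0:

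- S = 11: 45 − 4.5 = 40.5, a mean drop of 2.7 BPM
- S = 14: 90 − 18 = 72, a mean drop of 4.8 BPM
- S = 18: 150 − 50 = 100, a mean drop of 6.7 BPM

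The woman starting at 18 has half the recorded minutes and about 2.5 times the slowing of the woman starting at 11.

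**A milder illustration.** Suppose every woman takes a fixed g minutes to reach 9.5 BPM. Then E = 15 − g(S − 10)/(S − 9.5). Over 84 sessions, starts of 10.5, 14 and 18 give 1,050, 887 and 865 minutes for g = 5, and 924, 663 and 628 for g = 8. The direction is the same, but the gap is smaller for g = 5.

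**Across women.** Simulations assumed starting rates with mean 14 or 16 and SD 2 to 4, truncated at 10, and mean adherence of 85%. The rank correlation of total effective minutes with starting rate was negative in every scenario, from −0.06 to −0.94. The sign is stable and the size is not.

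**What adjustment for run-in rate does.**

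- If outcome truly depends on time at target, conditioning on a baseline variable leaves that slope unchanged.
- If outcome depends on slowing, then among women with the same start more minutes under 10 tend to go with more slowing, so part of the lost slope returns.
- If starting rate is prognostic, adjustment removes the false slope, provided its effect is modelled adequately.

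Simulation of these three cases showed the same pattern.

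**The case against.** The strongest objection is that the plan measures what it set out to measure. The intervention is defined by an absolute target, 5 to 10 BPM in sections B and D.1, so minutes under 10 are time at target. Women who slow a great deal without reaching 10 BPM have not received the intended exposure. That stands, and it is why the exposure should stay.

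Four stronger readings are tempting, and the document does not support them:

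- **The exposure ranks women wrongly and should be replaced by slowing.** This assumes that dose means fall from one's own rate, which D.10.4 does not say. The replacement also varies mechanically with starting rate, in the other direction: 40.5, 72 and 100 BPM-minutes in the illustration above. It contains the run-in rate, so error in that rate enters the exposure.
- **Sharing 10 BPM between entry and success is a mistake.** It is coherent, since it keeps out women already in the target range.
- **Ordinary variation yields effective minutes without any pacing.** Figures for this describe unpaced breathing. D.4.3 does not list the measure for the control device, so they would apply only to active-arm women who ignore the tones.
- **The trial itself links resting breathing rate to anxiety or autonomic state.** Its hypotheses concern the effect of slow breathing on those measures and their mediation of benefit, not resting rate as a predictor.

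Two further points stand. The 0.5 BPM per minute case is extreme: 18 BPM would need 16 minutes to reach 10, which fits poorly with a device set to pace below 10 BPM in 15-minute sessions. And cumulative minutes also vary with sessions completed, so the exposure does carry adherence information.

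**Conclusion.** The point holds as a refinement of an exploratory analysis. Given gradual slowing from the woman's own rate, minutes under 10 BPM depend on starting rate among equally adherent women, and the D.10.4 model has nothing to separate the two. The planned reading as adherence and exposure is therefore not clean.

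Dependence of the exposure on starting rate is shown. Distortion of the slope is only possible: blunting requires that benefit follow the amount of slowing, and bias requires that starting rate predict outcome. The document states neither.

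The size is undetermined. The per-session contrasts rest on assumed slowing speeds and perfect following, and the simulated correlations on assumed distributions. It would be wrong to conclude that the dose-response analysis is invalid or that its sign will reverse. The analysis is run only if benefit is found, and the primary ANCOVA is not affected.

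**What to change.** In D.10.4:

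1. Define effective practice as total minutes, over all downloaded sessions, with respiratory rate under 10 BPM, and keep it as the exposure.
2. Add mean breathing rate over the run-in sessions as a covariate next to the baseline outcome. D.6.4 requires practice on at least 6 run-in days, so this mean rests on several sessions.
3. As a sensitivity analysis only, use cumulative slowing: the sum over sessions of session minutes × (run-in mean rate − session mean rate). Adjust this for run-in rate too, because the drop contains it.

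The cost is a few sentences, one extra covariate, and some loss of precision if run-in rate and the exposure are strongly correlated. Session duration, session mean rate and run-in rate are already downloaded. The device, its target, eligibility and the primary analysis do not change. Writing this down before outcome data are examined also avoids a later choice among exposures.
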